IDUR	Investigational drug utilization record
IRB	Institutional review board
LDH	Lactic acid dehydrogenase
PCR	Polymerase chain reaction
PEG	Polyethylene glycol
PTP	Previously-treated patients
PUP	Previously-untreated patients
SD/HT	Solvent Detergent/Heat Treated
seronegative	non-reactive in an ELISA test for antibody to the virus in question
seropositive	reactive in an ELISA test for antibody to the virus in question
SWI	sterile water for injection
USP	United States Pharmacopeia
VWF	von Willebrand Factor

Contains Confidential and Proprietary Information of Grifols Inc.

PROTOCOL SUMMARY

Protocol Number:	GBI 04-01 (formerly ATC 02-01 of Alpha Therapeutic Corporation)
Title:	A Study of Immunologic Safety for Alphanate® in Previously Treated Patients Diagnosed with Severe Hemophilia A
Study Phase:	Phase IV
Study Duration:	At least 2 years
Name of Drug:	Antihemophilic Factor (Human), Alphanate® Solvent Detergent/Heat Treated
Drug Dosage:	An appropriate dosage for the prevention and/or control of bleeding
Concurrent Control:	None
Route and Form:	Intravenous
Objectives:	To determine the immunologic and general safety of long-term use of Alphanate® in individuals with severe hemophilia A.
Subject Population:	Males diagnosed with severe hemophilia A who have been previously treated with Factor VIII concentrates, cryoprecipitate, or whole blood for a total of 150 cumulative exposure days; at least six years and not more than 65 years of age, who have no history of exposure to Alphanate® and who have never been diagnosed with antibody inhibitors to Factor VIII or to nonspecific inhibitors of coagulation.
Structure:	Multi-center study
Blinding:	Unblinded
Method of Subject Assignment:	Non-randomized
Total Sample Size:	At least fifty evaluable subjects
Pharmacokinetics:	Not Applicable
Efficacy Endpoints	Not Applicable

Contains Confidential and Proprietary Information of Grifols Inc.

Primary Endpoint	1. The incidence of Factor VIII inhibitor development.
Secondary Endpoints:	
1. The frequency, nature, causality and severity of adverse events.2. The occurrence of changes in biochemical parameters which would indicate renal or hepatic impairment.3. The incidence of seroconversion to human immunodeficiency virus type 1 and 2 (HIV-1/HIV-2), hepatitis A virus (HAV), hepatitis B virus (HBV), hepatitis C virus (HCV) or parvovirus B19 in subjects seronegative for these viruses at the time of enrollment.4. The amount of product used per year as part of at-home prophylaxis and therapy for bleeding episodes.5. A physician's qualitative assessment of hemostasis (evaluated as "None", "Moderate", "Good", or "Excellent" in response to therapy with Alphanate[®] received by the subject in a hospital or another location under the physician's direct supervision.

Contains Confidential and Proprietary Information of Grifols Inc.

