4 STUDY DESIGN

This is a phase IV, non-randomized, multicenter study involving at least 50 evaluable subjects diagnosed with severe hemophilia A (levels of Factor VIII:C in plasma less than 0.01 IU/mL), who are male, at least six years of age and not more than 65 years of age, and with a Karnofsky Performance Score of at least 50. All subjects will have adequate immune system function (CD4 count must be greater than or equal to 400 cells/µL and subject must not have an immune system impairment or damage by disease or treatment).

Contains Confidential and Proprietary Information of Grifols Inc.

Enrolled subjects will be treated at home and with in-clinic therapy exclusively with Alphanate[®] as their sole source of FVIII concentrate for prophylaxis and treatment of all bleeding episodes and surgical procedures for a period of at least two years and a minimum of 50 exposure days, or, if 50 exposure days are not reached, for a maximum of 30 months. Alphanate[®] will be administered in accordance with the subject's usual pre-study treatment regimen. An exposure day is defined as any day on which a subject receives one or more infusions of any Factor VIII containing product. However, only one exposure day will be accrued for each surgical episode, regardless of the number of days of treatment or the number of infusions of Factor VIII associated with that surgical procedure.

A subject will continue treatment, as specified above, unless

- The subject develops inhibitors to Factor VIII at a titer greater than or equal to 5 Bethesda units (BU/mL);
- treatment with Factor VIII becomes ineffective at providing hemostasis even for a subject who has developed inhibitors with a titer of less than 5 BU/mL; or
- the subject exhibits severe or serious adverse events that prevent completion of participation in the study.

In all instances, only the inhibitor titer obtained by the central reference laboratory will be used to determine the subject's eligibility to continue his participation in the trial.

The primary endpoint of this study is:

the incidence of Factor VIII inhibitor after exposure to Alphanate[®].

The secondary endpoints are:

1. The frequency, nature, causality and severity of adverse events.
2. The occurrence of changes in biochemical parameters which would indicate alterations in renal or hepatic function.

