5.1 Inclusion Criteria

1. The subject must be male, at least six years of age and not more than 65 years of age.
2. The subject must have signed and dated an Informed Consent Form and Patient Authorization for Release of Information approved by the appropriate Institutional Review Board (IRB) prior to screening and enrollment. If the subject is a minor (*i.e.*, less than 18 years of age) both he and his parent or legal guardian must sign and date the informed consent.
3. The subject must have been diagnosed with severe hemophilia A and must have levels of Factor VIII less than 0.01 IU/mL.
4. The subject must have received treatment with cryoprecipitate, Factor VIII concentrates, and/or whole blood, for at least 150 cumulative exposure days (CEDs) prior to enrollment.
5. The subject must not have received treatment with cryoprecipitate, Factor VIII concentrate, or any other blood product, for at least 72 hours prior to screening.
6. The subject must never have been diagnosed with inhibitors to Factor VIII at any detectable titer.

Contains Confidential and Proprietary Information of Grifols Inc.

7. The subject must never have been diagnosed with nonspecific inhibitors of coagulation.
8. The subject must test negative for the presence of Factor VIII inhibitors at screening and enrollment.
9. The subject must have CD4 counts greater than or equal to 400 cells/ μ L.
10. The subject must have been vaccinated against hepatitis A and hepatitis B, or have evidence of antibodies against hepatitis A and hepatitis B. However, a subject who has no prior immunity against hepatitis A will be offered a course of vaccination for hepatitis A.
11. The subject must have a Kamofsky Performance Score of at least 50 (Appendix 1).

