7.4 Every 3 Months until Month 30 and/or Off-Study

Samples for quarterly testing will be drawn \pm **10 days** of the scheduled visit date. At each of these visits, the following procedures will be performed:

1. Abbreviated physical examination including: interim medical history, vital signs (pulse, respiratory rate, oral temperature, blood pressure) and weight;
2. Factor VIII coagulant activity (Factor VIII:C);
3. Factor VIII inhibitor levels (BU/mL) in two sets of samples;
4. Hematologic status will be assessed by: complete blood count (CBC) with white blood cell (WBC) differential and platelet count.
5. Serum chemistry tests including: alanine aminotransferase (ALT), aspartic aminotransferase (AST), alkaline phosphatase (AP), lactic acid dehydrogenase (LDH), blood urea nitrogen (BUN), creatinine and total bilirubin;
6. Viral and serological tests including: testing for HBsAg, and for antibodies to HAV, HBcAb, HBsAb, HCV, HIV-1/HIV-2 (only if seronegative at baseline) and parvovirus B19 by routine immunoassay (only in subjects who are seronegative at baseline);
7. A sample of venous blood will be drawn from which approximately 5 mL of serum will be prepared and aliquoted into three vials of at least 1.5 mL of sample each. The samples will be frozen and retained at -20°C in the event that they are required for later serological or virology tests.

If at any quarterly visit, **the subject tests positive for the presence of Factor VIII inhibitors (inhibitor titer of greater than 0.6 modified BU/mL), based upon the value determined by the central reference laboratory**, the procedures specified in section 7.12 (Subjects Who Develop Inhibitors) will also be performed.

Contains Confidential and Proprietary Information of Grifols Inc.

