9.2.2 Secondary Endpoints

1. Adverse Events

The percentage of subjects experiencing one or more adverse events will be calculated. The frequency of adverse events will be reported as a proportion of the total number of infusions with Alphanate®. Causality [the proportions of adverse events judged to be definitely, probably, possibly, probably not and definitely not related to treatments with Alphanate®] and severity will be reported as percentages of the total number of adverse events occurring during the course of the clinical trial.

2. Assessment of Biochemical Tests on Serum

Descriptive statistics will be presented, with a focus on parameters which when elevated may indicate alterations in hepatic or renal function.

3. Viral Safety

Viral safety will be determined by a lack of seroconversion to reactivity against the specific blood-borne viruses for which subjects will have been tested and found to be nonreactive at the time of enrollment.

4. Consumption Analysis

Descriptive statistics will be employed to evaluate the use of Alphanate® by subjects, both for self-administration and for treatment by the investigator at the clinical site or other places of treatment.

5. Hemostasis

Descriptive statistics will be employed to evaluate the physicians' qualitative assessments of the ability of Alphanate® to control bleeding episodes when administered at the clinical site.

Contains Confidential and Proprietary Information of Grifols Inc.

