9.2 Secondary Analyses

There are both efficacy and safety endpoints. All secondary safety analyses will be conducted on the Safety Population.

Secondary efficacy analyses will be summarized with categorical descriptive statistics for the following:

- The amount of product used per year as part of at-home prophylaxis and therapy for bleeding episodes, and
- A physician's qualitative assessment of hemostasis (evaluated as "None", "Moderate", "Good", or "Excellent" in response to therapy with Alphanate® received by the subject in a hospital or another location under the physician's direct supervision).

Secondary safety analyses will be summarized with categorical descriptive statistics for the following:

- The frequency, nature, causality and severity of adverse events,
- The occurrence of changes in biochemical parameters which would indicate renal or hepatic impairment,
- The incidence of seroconversion to human immunodeficiency virus type 1 and 2 (HIV-1/HIV-2), hepatitis A virus (HAV), hepatitis B virus (HBV), hepatitis C virus (HCV) or parvovirus B19 in subjects seronegative for these viruses at the time of enrollment,

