9.3 Additional Analyses

9.3.1 Exposure to Study Drug

Total exposure through the number of Factor VIII units infused will be summarized with descriptive statistics by dosing. Frequencies and percentages will also be used to summarize the number of infusions at each dosing.

Exposure to study drug will be listed for each subject to indicate the complete usage pattern including number of exposures at home and in clinic, reason for infusion, whether hemostasis was achieved (if evaluation available) and physician comments.

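### The yearly product-use endpoint has no stated unit, weight scaling or regimen split, and the SAP gives a continuous quantity categorical statistics

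*Protocol*

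**What the plan says.** The endpoint is "The amount of product used per year as part of at-home prophylaxis and therapy for bleeding episodes" (Protocol Summary, item 4; repeated in Protocol 4 and 8.2 and in SAP 2.3.1 and 9.2). No unit is attached to it anywhere.

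Three places say how product use will be summarised:

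- Protocol 9.2.2, item 4: "Descriptive statistics will be employed to evaluate the use of Alphanate® by subjects, both for self-administration and for treatment by the investigator". The only split named is who gives the infusion.
- SAP 9.2: "Secondary efficacy analyses will be summarized with categorical descriptive statistics for the following", and this endpoint heads the list. Under SAP 6.6, categorical data are summarised by frequencies and percentages; the mean, median, SD and range are for continuous data.
- SAP 9.3.1: "Total exposure through the number of Factor VIII units infused will be summarized with descriptive statistics by dosing". The grouping by dosing is not defined. The same section lists, subject by subject, "number of exposures at home and in clinic, reason for infusion, whether hemostasis was achieved", but plans no summary table by reason.

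SAP 6.2 plans no strata or covariates and SAP 6.3 no subgroups. SAP 8.3 summarises demographics for age and race only.

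On the population, Protocol 5.1 states "The subject must be male, at least six years of age and not more than 65 years of age", and Protocol 4 says that Alphanate "will be administered in accordance with the subject's usual pre-study treatment regimen".

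On the data, the home diary (Protocol 7.9.1) records date, units and reason for each infusion. Quarterly visits include "vital signs (pulse, respiratory rate, oral temperature, blood pressure) and weight". Weight is also taken at screening, enrollment and unscheduled visits. The schedule in Protocol Appendix 2 does not mark it for the 7-to-14-day visit or for in-hospital and in-clinic treatments.

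**The concern.** Consumption of a factor concentrate depends on how heavy the subject is, whether he is on prophylaxis, and how intensively he is treated. Only the last of these is informative about use of the product once the other two are known. The trial admits children and adults on whatever regimen they already had, so the first two will vary. The plan neither scales for weight nor separates the regimens.

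There is also a plain mismatch. An amount per year is continuous, yet the SAP text that names the endpoint prescribes frequencies and percentages, without giving categories. The one summary that would produce a mean in units is the general exposure table, which is not per year. Follow-up runs from two years to 30 months and some subjects will leave early, so a per-year figure needs a person-time denominator. None is given for this endpoint.

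At stake is whether a stated secondary endpoint, one of the two that the SAP classes as efficacy, can be read as consumption for prophylaxis or for bleeds.

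**Working it through.** **1. The protocol's own figure.** Protocol 7.9.2 gives dose = weight (kg) × 0.50 × desired increase (percent). Its example is 50 × 0.50 × 30 = 750 IU, which reproduces exactly. The documents give no computed figure for the consumption endpoint, so the rest is illustration. Target levels come from Protocol 7.9.2; weights and numbers of infusions are assumed.

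**2. Weight.** The prophylaxis guide is daily or every other day to about 0.15 IU/mL (15%).

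- Per infusion: 0.50 × 15 = 7.5 IU/kg.
- Every other day: 365 / 2 = 182.5 infusions a year, so 7.5 × 182.5 = 1,368.75 IU/kg/year.
- At 20 kg: 20 × 1,368.75 = 27,375 IU/year.
- At 80 kg: 80 × 1,368.75 = 109,500 IU/year.

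The ratio in units is 4.0; per kg it is 1.0. Among adults only, taken as 60 to 90 kg, it would be 90 / 60 = 1.5.

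**3. Regimen.** The guide for mild to moderate bleeds is a single infusion to 20–30%, that is 10 to 15 IU/kg. Assume 25 infusions a year (the 50-exposure-day minimum spread over two years).

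- Bleed treatment: 10 × 25 = 250 to 15 × 25 = 375 IU/kg/year.
- Prophylaxis: 1,368.75 (every other day) to 7.5 × 365 = 2,737.5 (daily) IU/kg/year.
- Ratios: 1,368.75 / 375 = 3.65, up to 2,737.5 / 250 = 10.95.

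If every bleed infusion went to 50%, the upper level given for more serious bleeds, use would be 25 × 25 = 625 IU/kg/year and the smaller ratio would fall to 1,368.75 / 625 = 2.19. These ratios are already per kg, so weight scaling does not remove them. Regimen needs its own split.

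**4. Both together.** Compare a 20 kg child on every-other-day prophylaxis with an 80 kg adult given 20 infusions a year to 25% (assumed).

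| | IU/year | IU/kg/year |
|---|---|---|
| Child, prophylaxis | 27,375 | 1,368.75 |
| Adult, on demand | 80 × 0.50 × 25 × 20 = 20,000 | 20,000 / 80 = 250 |
| Ratio | 1.37 | 5.48 |

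The unit figure can also hide a real difference in treatment intensity.

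**5. Share of the spread.** Write log yearly units as log weight + log yearly IU/kg + independent residual, with residual variance ln(1 + CV²). Assumptions: 10–50% children with weights uniform on 20–50 kg, adults uniform on 60–90 kg; 20–80% on every-other-day prophylaxis, the rest on 25 infusions a year to 30%; residual CV 30–100%. Over that grid, weight explains about 6% to 35% of the log-variance, and weight plus regimen about 33% to 88%.

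**The case against.** The strongest reply is that this is a descriptive secondary endpoint in a single-arm safety study whose Protocol Summary marks efficacy endpoints as not applicable. No test, comparator or decision rule depends on it, and the by-subject listing would let anyone reanalyse use by reason for infusion. That stands as a limit on importance. It does not make the planned summary interpretable: a listing is not a summary, and no planned table names weight.

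Several stronger readings are tempting, and the documents do not support them:

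- **That the plan fixes the endpoint as raw units per year, or adds the two uses together.** Neither is written. The unit is unstated, and the phrase names two uses without saying they are summed. The unit-based table in SAP 9.3.1 is total exposure.
- **That the figure would mainly reflect body size and regimen mix.** The documents give no weight distribution and no share on prophylaxis. Under the assumptions tried, the joint share ranges from a third to nearly nine tenths, and weight alone never exceeds about 35%.
- **That the result could not be compared with any other cohort.** The Protocol's Introduction cites a previously treated cohort using about 78,000 units per person per year, which is a raw-unit figure. A comparison is possible, though confounded by unknown differences in size and regimen. This is a reason to keep total IU/year.
- **That weight is available at every visit.** It is not scheduled at two of the visit types, though quarterly weights are enough for scaling.

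The dose formula is also a guide written for adults, with the dose left to the investigator. It serves here to show scale and does not predict what children in this trial would receive.

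A last objection is correct and changes the remedy. Splitting by reason for infusion alone would still pool, in the bleed-treatment row, subjects on prophylaxis with subjects treated on demand.

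**Conclusion.** The point holds as a matter of definition and summary. The endpoint lacks a unit, weight scaling and a denominator; SAP 9.2 gives it the wrong type of statistic, and its text does not fit the general descriptive plan in Protocol 9.2.2; no summary by regimen or reason is planned. That much rests on the documents alone.

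The size is illustrative. A pooled unit figure could differ 4-fold between 20 and 80 kg at identical IU/kg use (1.5-fold for 60 to 90 kg). It could differ about 3.7- to 11-fold between regimens at the guide levels with 25 bleed infusions a year, and less if bleeds are treated to higher levels. The weights, infusion counts and regimen shares are assumptions. What follows is that body size and regimen can strongly drive the result, not that they must dominate it.

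The consequence is confined to how this endpoint can be read. The inhibitor endpoint and the safety conclusions are untouched. The change is worth making because it is cheap and the data are already there.

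**What to change.** In Protocol 9.2.2 item 4 and SAP 9.2 and 9.3.1:

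- Define consumption as IU/kg/year. Divide each infusion's units by the most recent recorded weight (screening, enrollment, quarterly or unscheduled visit), sum, and divide by the subject's time on study. The on-treatment period in SAP 7.3 could serve as that time.
- Replace categorical with continuous descriptive statistics for this endpoint. Leave the hemostasis rating categorical.
- Report prophylaxis and bleed treatment separately by the recorded reason for infusion. State where infusions before physiotherapy or surgery go, since Protocol 7.9.1 lists them as an indication of their own.
- State the denominator of the prophylaxis row (all subjects, or only those on prophylaxis).
- Show the bleed-treatment row separately for subjects on prophylaxis and subjects treated on demand, with a stated rule for classifying regimen.
- Keep total IU/year alongside, so that it can be set against the raw-unit figure in the Protocol's Introduction.

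The cost is a wording change in both documents and a little extra programming. Because the Protocol text changes, the amendment needs the IRB review required by Protocol 13.1. No dose, visit or primary analysis is affected, and weight, units and reason for infusion need no new collection.

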1 INTRODUCTION

The development of an immune response to Factor VIII (*i.e.*, the generation of antibody inhibitors of Factor VIII) by patients diagnosed with hemophilia A and treated with Factor VIII concentrates is a serious complication in the treatment of hemophilia A.^{1,2} Estimates of inhibitor formation from retrospective and prospective clinical trials vary from as low as four percent to as high as 28 percent. All studies agree that prevalence of antibody inhibitors is higher among individuals with severe hemophilia A (Factor VIII:C less than 0.01 IU/mL) than among individuals with mild or moderate disease, with estimates ranging from eight to 28 percent.^{3,4}

In clinical trials in which previously-untreated or minimally-treated patients (PUPs) were treated with recombinant Factor VIII concentrates, the incidence of inhibitors to Factor VIII was measured as a function of cumulative exposure days (CEDs). In a clinical trial conducted by Bray *et al.*⁵, inhibitors developed in 17 of 71 (24%) PUPs treated with Recombinate® (Baxter Bioscience); 5 of the 71 (7%) patients developed high-responder inhibitors. The median number of CEDs was 11 for all patients and nine for patients who developed inhibitors.

Similarly, in a clinical trial conducted by Lusher *et al.* of subjects receiving Kogenate® (Bayer), inhibitor formation occurred in 16 of 62 (27%) subjects.⁶ Seven of the 62 (11%) patients developed high-responder inhibitors. The median number of CEDs was nine for patients who developed inhibitors and 28 for subjects who exhibited no immune response to Kogenate®.

Several clinical trials have been conducted in which PUPs were enrolled and then treated with plasma-derived Factor VIII concentrates of varying purity and produced using differing virucidal treatments (*e.g.*, terminal dry heat, pasteurization, solvent-detergent).⁷⁻⁹ The rates of incidence for antibody inhibitors ranged from 21 to 28 percent, a range similar to that observed with recombinant Factor VIII products. Consequently, the investigators for these trials concluded that recombinant DNA products do not pose any greater risk for inhibitor formation in PUPs than do plasma-derived products.

However, a substantially increased incidence of Factor VIII inhibitors (a 4.5-fold increase) was reported by Peerlinck *et al.*¹⁰ and Rosendaal *et al.*¹¹ in clinical trials of previously treated individuals (PTPs) treated with pasteurized factor VIII concentrate of an intermediate purity that is available in Europe. The increase in inhibitor formation was observed even in individuals who had been previously treated with multiple Factor VIII products ("multitransfused" patients). The authors suggested that pasteurization might have compromised the integrity or conformation of Factor VIII, which in turn could have resulted in increased immunogenicity.

Contains Confidential and Proprietary Information of Grifols Inc.

Guérois *et al.*¹² conducted a clinical trial involving 56 PUPs treated with HPSD-VIII® (a plasma-derived, high-purity, solvent-detergent treated concentrate). The incidence of immune response was monitored over a period of 76 months (median = 29 months) and for patients experiencing 100 CEDs (median = 26 CEDs). The median number of CEDs prior to detection of inhibitors was 16 days. Inhibitors developed in five patients (9 percent), only one of whom was categorized as a high responder (2 percent). Therefore, it appeared that the use of HPSD-VIII® was associated with a lower incidence of antibody inhibitor than was observed with the administration of recombinant DNA products or a combination of plasma-derived concentrates. Additionally, inhibitors appeared later (16 CEDs) in individuals receiving HPSD-VIII® than in those treated with the recombinant DNA products (nine CEDs).

Addiego *et al.*¹³ investigated the use of Hemofil M®, a plasma-derived Factor VIII concentrate treated with a solvent-detergent process, in 23 PUPs. Only two of 23 (9%) patients developed inhibitors after 14 to 26 CEDs. Although the number of subjects was limited in this trial, the median number of CEDs experienced by this population, 32 days, exceeded those in the populations studied by Guérois *et al.*¹², Bray *et al.*⁵ and Lusher *et al.*⁶ A more limited study by Lusher and Salzman with the pasteurized Factor VIII concentrate Monoclate P® showed an incidence of inhibitor formation of 18 percent.¹⁴

A study of the incidence of inhibitors in previously-treated patients (PTPs) carried out by McMillan *et al.* included 1306 hemophilia patients whose mean age was 18, and who were followed for up to four years. Thirty-one of these individuals (2.4 percent) developed inhibitors to Factor VIII; of these, 29 had been diagnosed with severe hemophilia A. The incidence of new inhibitors was eight per 1,000 patient-years of observation.

In a study of PTPs treated with recombinant Factor VIII (Kogenate®), by Schwartz *et al.*, inhibitor formation was observed in only 1 of 86 (1.2%) patients following repeated exposure to the product.¹⁶ The mean annual per capita consumption of Factor VIII in this subgroup was estimated to be approximately 78,000 units annually.

